9.2.7 Immunohistochemistry

In addition, immunohistochemistry will be performed on all specimens to better examine the effect leflunomide has on the changing tumor and tumor microenvironment as well as correlate these findings with those from scRNA-seq. Current work in this area has noted that the predominant cells in the tumor microenvironment of CD30+LYPDs include CD163+ M2, tumor infiltrating CD8+ lymphocytes, FOXP3+ Tregs and programmed cell death (PD-1) lymphocytes.

The multiplex immunohistochemistry of the tumor microenvironment will distinguish the CD30+ T cells (tumor cells) from other cells (M2, Tregs, tumor infiltrating T cells) and whether or not PD1 co-expression is noted. The findings will be correlated to clinical response.

10.0 STUDY CALENDAR

Table 10 describes required procedures. All procedures may increase in frequency if clinically indicated or oriented following toxicity. Adjustments to the treatment cycle due to a hold in study agent are detailed in [Section 5.2](#).

Table 10.0 Study Activity Calendar

	Screen -ing ^a	Cycle 1, 2, 3		Cycle 4+ Day 1 ^d	End of Treatment ^e				Active Follow-Up ^j
		Day 1 ^b	Day 14 ^c		Day 0 ^f	Days 1-11 ^g	Day 14 ^h	Day 30 ⁱ	
Informed Consent ^k	X ^s								
Inclusion/Exclusion Criteria ^l	X								
Registration ^m	X ⁿ								
Medical history ⁿ	X								
Physical exam	X	X		X				X	
Vital signs ^o	X	X		X				X	
Adverse events assessment ^p		X	X	X	X	X		X	
Concomitant meds review	X	X		X	X			X	
ECOG status (Appendix A) ^q	X	X		X				X	
Pregnancy test ^q	X								
TB antigen test ^r	X								
Hepatitis A, B, C testing	X ^s								
Skin photographs ^t	X	X		X	X			X	X
mSWAT ^u	X	X		X	X			X	X
Skin biopsy ^v		X ^w		X ^w				X ^w	
CBC with differential ^x	X	X	X	X				X	X
Chemistry panel ^y	X	X	X	X				X	X
Response assessment ^z		X		X	X			X	X
Teriflunomide clinical testing ^{aa}				X			X ^{dd}	X ^{dd}	
Leflunomide administration ^{bb}		Daily							
Cholestyramine ^g						X ^g			

- a. All screening procedures to be performed within 21 days of start of study agent except informed consent, acute hepatitis panel, skeletal survey which may occur within 30 days of start of treatment (footnote u) and except for registration which must occur within 7 days from start of treatment (footnote n).
- b. Day 1 assessments to be performed within 5 days (120 hours) prior to Day 1 drug (except footnote u for C1 only). Day 1 safety assessments must be resulted and reviewed prior to administration of agent for the cycle that is initiating. Screening assessments, if performed within this aforementioned time frame, may serve as C1D1 assessments. Note: items with footnote "aa" are not performed for C1D1; the windows for screening assessments still apply.
- c. Day 14 evaluations have +/- 3 day window.
- d. Day 1 assessments to be performed within 5 days (120 hours) prior to Day 1 drug. Day 1 safety assessments must be resulted and reviewed prior to administration of agent for the cycle that is initiating.
- e. Reasons to end study treatment include disease progression and unacceptable toxicity. See Section 5.8 for all criteria.
- f. End of Treatment (EOT) Day 0 is defined as the day the determination to end treatment is made. EOT Day 0 assessments to be performed as soon as feasible, especially in the event of off treatment due to unacceptable toxicity and no later than 7 days after decision to end treatment; assessments performed after last dose of study agent(s) and within 7 days of the decision to end treatment may serve as EOT Day 0 assessments.
- g. EOT Day 1 is defined as the day cholestyramine administration begins; it will usually follow immediately after EOT Day 0, although it will not be deviation if this does not occur. If it does not follow immediately after EOT Day 0, the rest of calendar will follow per the actual EOT Day 1 (not EOT Day 0). Cholestyramine (8 grams three times daily for 11 days) will be administered according to [Section 5.5](#).
- h. EOT Day 14 assessments must occur after completion of cholestyramine, and may occur on Day 14 +/- 3 day window. If the cholestyramine administration period is extended beyond 11 consecutive days, the EOT Day 14 assessments may occur outside of this defined window.
- i. EOT Day 30 visit has a +/- 2 day window, however this window may be adjusted without deviation to ensure that it corresponds to the final teriflunomide clinical test (see footnote ee). All participants will be followed until resolution or stabilization of any serious adverse events occurring during treatment or starting within 30 days of last study drug administration or within the time to complete the EOT Day 30 assessments, which every occurs later.
- j. Active follow-up will occur for participants who have completed EOT procedures and yet to demonstrate disease progression. Disease response will be assessed every 3 months. Active follow-up will continue for 12 months or until disease progression, whichever is earlier.
- k. Informed consent process to be fully documented: e.g. prospective participant had sufficient time for deliberation, all questions were answered, treatment options provided by MD, full study reviewed including risks, and a copy of signed consent given to participant.
- l. Inclusion/exclusion criteria are detailed in [Section 3](#).
- m. See [Section 4.3](#) for slot reservation and registration process. Treatment must begin within 7 days of registration. Documentation providing Investigator's confirmation that all eligibility criteria are met must be available prior to registration.
- n. Medical history to include review treatment history for CD30+LYPD medical history pertaining to eligibility, and demographic information.
- o. Vital signs: Weight, heart rate, blood pressure, respiration rate, temp. Height required only at baseline.

- p. Adverse event (AE) reporting begins for events that occur after start of study agent. AE recording and reporting will continue until the completion of the EOT Day 30 visit or until resolution or stabilization of any serious AE occurring before the completion the EOT Day 30 assessments, which every occurs later.
- q. Serum or urine pregnancy test for women of child bearing potential only.
- r. T-Spot or other TB antigen test.
- s. Consent, acute hepatitis panel, to be completed within 30 days prior to registration.
- t. Skin photographs: for subjects with skin lesions, up to five designated index lesions, representative of the subject's extent of disease, will be selected at baseline and measured and photographed using a digital camera. Photos should be taken against a blue backdrop. The photos will be taken on Day 1, prior to the first dose and then Cycle 2 Day 1 (-7 days) then every Cycle. In addition, half-body global photos (waist to feet, waist to top of head and sides) will also be obtained. Photos must be labeled with patient's protocol number and initials.
- u. Modified Severity Weighted Assessment Tool (mSWAT)[30] ([Appendix C](#))
- v. skin biopsies for research will not be taken at baseline if patients have a recent biopsy taken containing needed information.
- w. skin biopsies for research at baseline, at C2D1, C5D1, and EOT (if lesions are present), and at disease progression ([Section 9.2](#)).
- x. CBC with differential: erythrocytes (RBC), hemoglobin, hematocrit, platelets, total WBC plus absolute differential counts (neutrophils, lymphocytes, monocytes, eosinophils, basophils).
- y. Serum chemistry panel: Comprehensive metabolic panel (sodium, potassium, chloride, carbon dioxide, creatinine, urea nitrogen, calcium, glucose, albumin, total bilirubin, alkaline phosphatase, total protein, ALT/SGPT, AST/SGOT) LDH, magnesium, phosphorus, and uric acid.
- z. See [Section 11.2](#) for response assessment criteria.
- aa. Teriflunomide clinical blood assay to be ordered as "leflunomide metabolite" miscellaneous clinical test.
- bb. Clinical testing must demonstrate teriflunomide plasma levels less than 0.02 mg/L or 0.02 µg/ml by two separate tests at least 14 days apart. If plasma levels are higher than 0.02 mg/L or 0.02 µg/mL, additional cholestyramine treatment will be considered.
- cc. Participants will receive leflunomide orally on a daily basis which will be recorded on the pill diary ([Appendix D](#)). The first 3 loading doses will be given at a dose of 100 mg, after which treatment will continue at a dose of 20 or 10 mg daily. See administration details in [Section 5.3](#).

11.0 ENDPOINT DEFINITIONS/MEASUREMENT OF EFFECT

11.1 Safety Endpoints

Toxicity will be graded according to the NCI-Common Terminology Criteria for Adverse Events version 5.0.

11.2 Efficacy Endpoints

Response on this study will be assessed by mSWAT (see Appendix C). In addition to mSWAT, individual lesions will also be assessed by the Composite Assessment of Index Lesion Severity (CAILS) tool (see [Appendix E](#)).

Overall Response Rate:

- Defined as the proportion of patients with a documented response (CR or PR) any time during study treatment.

Complete Response Rate:

- Defined as the proportion of patients with a documented CR any time during study treatment.

Duration of response:

- Defined as the time interval from the date of first documented response (CR or PR) to the first documented disease progression or death, whichever occurs first. Patients without a documented CR or PR will be excluded. Patients who do not achieve CR or PR are excluded from this analysis.

11.3 Exploratory Endpoints

Endpoints for the exploratory objective on RNA signature are the RNA expression levels.

12.0 STATISTICAL CONSIDERATIONS

12.1 Study Design

This study will be conducted as a single center pilot study to obtain some preliminary data on leflunomide treatment for patients with cutaneous LYPD. Patients will receive up to 13 cycles of leflunomide until any criterion for off-treatment is met. Patients without progressive disease at the time of off-treatment will be followed for up to 1 year after off-treatment as active follow-up. Response will be assessed after every cycle per mSWAT while on treatment and every 3 months while in active follow-up. The primary endpoint is overall response rate. Secondary endpoints include complete response rate, duration of response, and toxicities.

12.2 Sample Size and Accrual Rate

This study will accrue 12 response evaluable patients, with a maximum accrual of 14 patients. Because this is a rare disease that has not been systematically studied in a prospective clinical trial, there is a lack of historical data on the response rate (and by mSWAT) in this patient population. The sample size for this pilot study was chosen based on feasibility considerations, and not based on any definitive statistical criterion. With 12 patients, the 95% exact binomial confidence interval for the overall response rate will have a width of 55% (33% response rate, with 4 responders), 57% (42% response rate, with 5 responders),

58% (50% response rate, with 6 responders), 57% (58% response rate, with 7 responders), 55% (67% response rate, with 8 responders), 52% (75% response rate, with 9 responders), and 46% (83% response rate, 10 responders) respectively. For any AE with a true incidence of 15% or higher, with 12 patients there is at least an 86% chance of observing 1+ patients with such AE.

We project to accrue approximately one patient every 3 months. The projected study accrual duration is therefore 3 years.

12.3 Evaluable Participants and Participant Replacement

All participants who received at least 1 dose of study drug will be evaluable for toxicity. All participants who received at least 1 dose of protocol leflunomide and had at least 1 post-baseline response assessment will be evaluable for response; patients inevaluable for response (for example patients who did not receive any protocol treatment, or patients who had no response assessment on study due to withdrawal of consent during cycle 1) will be replaced.

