With 12 patients, the 95% exact binomial confidence interval for the overall response rate will have a width of 55% (33% response rate, with 4 responders), 57% (42% response rate, with 5 responders), 58% (50% response rate, with 6 responders), 57% (58% response rate, with 7 responders), 55% (67% response rate, with 8 responders), 52% (75% response rate, with 9 responders), and 46% (83% response rate, 10 responders) respectively. For any AE with a true incidence of 15% or higher, with 12 patients there is at least an 86% chance of observing 1+ patients with such AE.

We project to accrue approximately one patient every 3 months. The projected study accrual duration is therefore 3 years.

Analysis: Observed toxicities will be summarized in terms of type (organ affected or laboratory determination), severity, attribution, time of onset, duration, serum concentration of the active leflunomide metabolite, probable association with the study treatment and reversibility or outcome. Baseline information (e.g. the extent/type of prior therapy) and demographic information will be presented as well to describe the patients treated in this study.

Rates and 95% Clopper Pearson binomial confidence interval (CI) will be calculated for overall response rate (patients that have confirmed CR or PR) and clinical benefit rate (patients that have confirmed CR/PR/MR or SD). In addition, sub-analyses will be performed where participants will be considered evaluable for response if they are confirmed eligible, receive at least 75% of leflunomide during the first cycle of therapy and have their disease re-evaluated. Response rates will also be explored based on number/type of prior therapy(ies) and serum concentration of the leflunomide metabolite (μ g/mL). Time to response and survival will be estimated using the product-limit method of Kaplan and Meier.

Preliminary molecular profiles for mRNA will be derived from skin biopsies. These profiles will be used to identify molecular correlates of therapeutic response using pathway identification and supervised principal components analysis.

Abbreviated Eligibility Criteria

Main Inclusion Criteria

- Adult patients with a diagnosis of CD30+LYPD with life expectancy of > 3 months
- ECOG ≤2
- Relapsed or refractory to at least 1 prior line of therapy
- Platelet count \geq 50,000/ μ L, ANC \geq 1000/mm³, AST and ALT < 2.0 x ULN, total bilirubin < 1.5 x ULN

Main Exclusion Criteria

- Prior treatment with lenflunomide

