12.4 Statistical Analysis Plan

Patient demographic and baseline characteristics, including age, gender, medical history, and prior therapy, will be summarized using descriptive statistics. For continuous variables, descriptive statistics (number [n], mean, standard deviation, standard error, median, and range will be provided. For categorical variables, patient counts and percentages will be provided.

Observed toxicities will be summarized, in terms of type, grade, time of onset, duration, and attribution to the study treatment. The overall response rate and complete response rate will be calculated along with the Clopper Pearson binomial 95% exact confidence intervals. Duration of response will be calculated using Kaplan-Meier product limit estimator; median duration of response will also be estimated when possible.

The miRNA/mRNA expression profile data will be summarized by descriptive statistics. The data will also be used to explore the miRNA/mRNA that show significant differences between responders and non-responders after leflunomide treatment. For miRNA/RNA profiling, fold changes >3 with an FDR <0.05 will be considered significant.

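### The denominator of the primary response rate is not stated, and the set the plan implies drops treated patients who were never assessed, which can only leave the rate unchanged or raise it

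*Combined protocol and SAP*

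**What the plan says.** Section 11.2 defines the ORR as the "proportion of patients with a documented response" (CR or PR) during study treatment, and the complete response rate in the same way. It does not say which patients are counted. Section 12.4 says only: "The overall response rate and complete response rate will be calculated along with the Clopper Pearson binomial 95% exact confidence intervals". No analysis set is named there either.

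The nearest thing to a denominator is in 12.2 and 12.3. Section 12.2 states: "This study will accrue 12 response evaluable patients, with a maximum accrual of 14 patients". It then gives exact interval widths for the ORR with 12 patients. Section 12.3 makes a patient evaluable for response after at least one dose of leflunomide and at least one post-baseline response assessment. Patients who fail this are replaced. The examples given are patients who were never treated and "patients who had no response assessment on study due to withdrawal of consent during cycle 1) will be replaced".

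For safety, 12.3 uses a wider set: "All participants who received at least 1 dose of study drug will be evaluable for toxicity".

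The synopsis (Statistical Considerations) gives the ORR and its interval without naming a set, and then continues: "In addition, sub-analyses will be performed where participants will be considered evaluable for response if they are confirmed eligible". That narrower set also requires at least 75% of cycle 1 leflunomide and a disease re-evaluation. Section 12.4 does not repeat this sub-analysis.

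**The concern.** In a single-arm pilot whose primary result is one proportion and its interval, the denominator should be fixed before data are seen. Here more than one choice fits the text. Sections 12.2 and 12.3 point to the response-evaluable set. The synopsis presents its 75% set as an addition, so the main set must be something else, but it does not say whether that is the 12.3 set or a wider one. An all-treated ORR is neither ruled out nor stated.

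The implied choice also works in one direction. The replacement rule treats two different groups alike. Patients who never took the drug do not belong in an all-treated estimate, so replacing them does no harm. Patients who took the drug and left before any assessment do belong in it, and the rule removes them from the ORR and fills their places. Because 12.3 gives consent withdrawal only as an example, the exclusion also covers loss to follow-up or death before the first assessment.

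**Working it through.** **Inputs**

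- Target of 12 response-evaluable patients, maximum accrual 14 (12.2).
- Evaluable for response: at least 1 dose and at least 1 post-baseline assessment (12.3).
- Numerator: documented CR or PR (11.2); the synopsis says confirmed.
- Interval: two-sided 95% Clopper-Pearson (12.4). For x responders of n, the lower limit is the 2.5% quantile of Beta(x, n − x + 1) and the upper limit is the 97.5% quantile of Beta(x + 1, n − x).
- Assumption: k, the number of treated patients with no post-baseline assessment. The documents give no expected value. If 12 evaluable patients are reached under the cap of 14, k is 0, 1 or 2.

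**Step 1. Reproduce the plan's widths (n = 12)**

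| Responders | 4 | 5 | 6 | 7 | 8 | 9 | 10 |
|---|---|---|---|---|---|---|---|
| Stated width (%) | 55 | 57 | 58 | 57 | 55 | 52 | 46 |
| Computed width (%) | 55.19 | 57.17 | 57.81 | 57.17 | 55.19 | 51.70 | 46.33 |

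All seven agree. The response rates printed beside them (33% with 4 responders, and so on) are x/12, so the precision statement is counted in 12 patients.

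**Step 2. Direction**

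A treated patient with no post-baseline assessment cannot have a documented response, so x is the same in both sets. The gap is x/12 − x/(12 + k) = xk / [12(12 + k)]. It is never negative, and it is zero only if x = 0 or k = 0.

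**Step 3. Size when 12 evaluable patients are reached**

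| Responders | Evaluable set, n = 12 | All treated, n = 13 (k = 1) | All treated, n = 14 (k = 2) |
|---|---|---|---|
| 4 | 33.3% (9.9–65.1) | 30.8% (9.1–61.4) | 28.6% (8.4–58.1) |
| 6 | 50.0% (21.1–78.9) | 46.2% (19.2–74.9) | 42.9% (17.7–71.1) |
| 8 | 66.7% (34.9–90.1) | 61.5% (31.6–86.1) | 57.1% (28.9–82.3) |
| 10 | 83.3% (51.6–97.9) | 76.9% (46.2–95.0) | 71.4% (41.9–91.6) |

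At 6 responders the gap is 6 × 1 / (12 × 13) = 3.8 points for k = 1 and 6 × 2 / (12 × 14) = 7.1 points for k = 2. Over the plan's range of 4 to 10 responders it is 2.6 to 6.4 points for k = 1 and 4.8 to 11.9 points for k = 2.

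**Step 4. If 12 evaluable patients are not reached**

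With 11 evaluable of 14 treated, 6/11 = 54.5% against 6/14 = 42.9%, a gap of 11.7 points (7.8 to 19.5 for 4 to 10 responders). The k = 2 figures are therefore not an upper bound.

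**Step 5. Precision on an all-treated denominator**

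The maximum exact width over all responder counts is 57.8% for n = 12 (at 6 responders), 55.6% for n = 13 (at 6 or 7) and 53.9% for n = 14 (at 7).

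**Step 6. Who is actually exposed**

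Table 10 schedules a response assessment on Day 1 of each cycle, at EOT Day 0 and at EOT Day 30. Footnote f reads: "EOT Day 0 assessments to be performed as soon as feasible, especially in the event of off treatment due to unacceptable toxicity". Footnote i reads: "EOT Day 30 visit has a +/- 2 day window". Section 17.5 lets a patient stop treatment and continue study procedures. A patient who stops early for toxicity or progression but still attends therefore stays evaluable and counts as a non-responder. The exposed group is mainly patients who withdraw fully, or are lost, before any assessment.

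**The case against.** The best counter-argument is that the denominator is effectively known. Section 12.2 divides by 12, 12.3 says who the 12 are, and no text proposes a wider set for the ORR, so all that is missing is a cross-reference in 12.4. The 12.3 rule is also lenient, because one dose and one assessment suffice. With the end-of-treatment assessments, the usual route to bias, dropping early failures, is largely closed. The one or two unassessed patients are hypothetical, and the two spare places also cover patients never dosed, who cause no gap. The 11-of-14 case needs 3 of 14 treated patients (21%) to go unassessed. There is no null rate, success threshold or go/no-go rule, and a shift of 3.8 points sits inside an interval 57.8 points wide. On this view, naming the set in 12.4 is enough, with an all-treated ORR as an optional sensitivity analysis.

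Much of this stands. Exposure is limited, the size is conditional, and no test or error rate is affected. The 11-of-14 case shows only that two patients is not a limit; it is not an expected outcome.

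It does not remove the point. A set that has to be inferred from the sample-size section is not a stated analysis set for the primary endpoint. The interval describes sampling error and does not cover a selection effect that runs one way. At n = 12 each responder is worth 1/12 = 8.3 points, so a single exclusion is visible. Naming the 12.3 set would remove the ambiguity but leave the one-directional exclusion in place.

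**Conclusion.** The concern holds. The plan does not state the denominator of its primary ORR or of the complete response rate, and the set it implies omits treated patients with no post-baseline assessment. Relative to all treated patients, this leaves the ORR unchanged or raises it. That direction is exact, because only documented responses count.

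The size rests on an assumed number of unassessed treated patients. It is nil with none. If 12 evaluable patients are reached, then over 4 to 10 responders it is 2.6 to 6.4 points with one such patient and 4.8 to 11.9 points with two. It can be larger if the target of 12 is missed. The effect falls on the estimate and its interval, not on a decision rule. The plan should be changed, because the remedy is cheap and the estimate is the trial's main product. Confidence is medium: the omission is certain, but whether it will matter depends on early losses that the documents do not predict.

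**What to change.** - In 12.3 and 12.4, define the denominator of the primary ORR and of the complete response rate as all patients who received at least one dose of leflunomide, the set 12.3 already uses for toxicity. Count those with no post-baseline assessment as non-responders.
- Report the 12.3 response-evaluable set as a labelled supportive analysis. Keep the synopsis 75% set as the sub-analysis it already is.
- Replacement to reach 12 evaluable patients within the cap of 14 can continue, but state that a treated patient who is replaced stays in the primary denominator.
- Make matching edits in 12.2 and the synopsis. Extend the precision statement there to the maximum exact widths for 12, 13 and 14 treated patients (57.8%, 55.6% and 53.9%). This last edit is useful but not essential, since the stated 58% already covers the widest case.

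The cost is wording in four places and IRB review of the revision (17.3). No patients or visits are added. The reported ORR may be a few points lower, and it will be conservative if unassessed patients left for reasons unrelated to outcome. The supportive analysis lets the reader see that.
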